2 STATISTICAL AND ANALYTICAL PROCEDURES

2.1 ANALYSIS ENDPOINTS

2.1.1 Demographic and baseline characteristics

The baseline value (with the exception of serum creatinine and eGFR) is defined as the last available value before the first dose of double-blind investigational medicinal product (IMP) or the last available value prior to randomization for patients who were randomized but never exposed to IMP.

For serum creatinine and eGFR, the baseline value is defined as the average of all values before the first dose of double-blind IMP for those randomized and exposed or before randomization for those who were randomized but never exposed to IMP.

Baseline safety and efficacy parameters are presented along with the summary statistics for safety and efficacy sections ([Section 2.4.5](#) and [Section 2.4.4](#)).

Demographic characteristics

Demographic variables to be summarized are:

- Age (years): Year of informed consent - Year of birth.
- Age categories (<50, ≥50 to <65, ≥65 to <75, ≥75 years).
- Gender (Male, Female).
- Race (White, Black or African American, Asian, American Indian or Alaska native, Native Hawaiian or other pacific islander, Multiple, Unknown).
- Ethnicity (Hispanic or Latino, Not Hispanic or Latino, Unknown).
- HbA1c (%) at screening visit.
- Randomization strata of HbA1c (≤8.5%, >8.5%) at screening visit (data from IRT).
- Mean SBP at screening visit.
- Randomization strata of mean SBP (<130 mmHg, ≥130 mmHg) at screening visit (data from IRT).
- eGFR (mL/min/1.73m²) at screening visit.
- Randomization strata of CKD stage (3A, 3B) at screening visit (data from IRT).
- Baseline body mass index (BMI) (kg/m²) derived as: (Weight in kg)/(Height in meters)².
- Baseline BMI categories (<30, ≥30 kg/m²).
- Country.

Disease characteristics at screening or baseline

Disease history includes:

- Duration of diabetes (years): (Date of informed consent - Date of diagnosis of diabetes + 1)/365.25.
- Duration of diabetes categories: (<10, ≥10 years).
- Age at diagnosis of diabetes (years): Year of diagnosis of diabetes - Year of birth.
- Prior use of sodium-glucose cotransporter type 2 (SGLT2) (Yes, No).
- Prior antidiabetic medication (in monotherapy or combination):
 - Insulin,
 - SU and/or glinide,
 - Metformin,
 - OADs other than SU, glinide and metformin,
 - GLP-1 receptor agonist.
- Prior antidiabetic medication :
 - No antidiabetic therapy,
 - Insulin (alone or with other antihyperglycemic agents),
 - SU and/or glinide (alone or with other non-insulin antihyperglycemic agents),
 - Other (non-insulin antihyperglycemic agents except SU and glinide).
- Baseline diabetic microvascular complications (Yes, No) (ie, diabetic retinopathy, diabetic neuropathy, diabetic nephropathy [duration of diabetic nephropathy for patients with diabetic nephropathy], diabetic peripheral neuropathy [sensory or motor], diabetic autonomic neuropathy, and diabetic foot infection).
- Baseline UACR categories (<30 mg/g [Normal], ≥30 to <300 mg/g [Microalbuminuria], and ≥300 mg/g [Macroalbuminuria]).
- Prior antihypertensive medication identified by therapeutic class as agents acting on the renin-angiotensin system, beta blocking agents, diuretics (a sub-category: loop diuretics identified by pharmacological class as high-ceiling diuretics), calcium channel blockers, and antihypertensives according to World Health Organization-Drug Dictionary (WHO-DD).

Medical or surgical history

Medical history and medical findings include:

- Physical examination.
- Medical or surgical history.
- Medical history cardiovascular.
- Surgical history amputation.
- Alcohol habits.

- Tobacco smoking habits.

Medical and surgical history will be coded to a “lower level term (LLT)”, “preferred term (PT)”, “high level term (HLT)”, “high level group term (HLGT)”, and associated primary “system organ class (SOC)” using the version of Medical Dictionary for Regulatory Activities (MedDRA) currently in effect at Covance at the time of database lock.

Any technical details related to computation, dates, and imputations for missing dates are described in [Section 2.5](#).

2.1.2 Prior or concomitant medications

All medications taken in the 3 months before the screening visit (any time for prior SGLT2) until the end of the study are to be reported in the electronic case report form (e-CRF).

All medications will be coded using the World Health Organization-Drug Dictionary (WHO-DD) using the version currently in effect at Covance at the time of database lock.

- Prior medications are those the patient used prior to first administration of double-blind IMP. Prior medications can be discontinued before first administration or can be ongoing during treatment phase.
- Concomitant medications are any treatments received by the patient concomitantly to the IMP, from the first administration of double-blind IMP to the date of the last administration of double-blind IMP + 10 days. A given medication can be classified both as a prior medication and as a concomitant medication.
- Posttreatment medications are those the patient took in the period running from the 11th day after the last administration of double-blind IMP up to the end of the study.

Any technical details related to computation, dates, imputation for missing dates are described in [Section 2.5](#).

2.1.2.1 Rescue therapy

Open label rescue medication(s) to treat hyperglycemia must be in accordance with local standard of care and prescribing practice for patients with CKD and will be at the discretion of the Investigator. Except for SGLT2 inhibitors and medications with specific contraindications in renal impairment, any approved medication(s) including oral antidiabetic drugs or insulin can be considered with appropriate dose modification as indicated. Rescue therapy is considered as a non-investigational medicinal product (NIMP).

2.1.2.2 Prohibited prior and concomitant medications

During the study treatment period, the following medications are prohibited:

- Initiation of any antidiabetic agents, including oral or injectable antihyperglycemic agents other than the IMP and NIMP is not allowed before the rescue therapy. The existing background medication (NIMP) should not be modified before the rescue.
Note: short term use (<10 consecutive days) of the prohibited medication, eg, short-acting insulin for treatment of acute illness or surgery is allowed.
- SGLT2 inhibitors (eg, canagliflozin, dapagliflozin, or empagliflozin) are not allowed for rescue.
- Systemic use of glucocorticoids for more than 10 consecutive days (topical, intra-articular, ophthalmic, nasal spray or inhaled applications are allowed).
- Investigational medicinal products in any other clinical study.
- Modification of antihypertensive medication before Week 12 is not allowed unless for safety reasons.
- Initiation of any weight loss drugs (eg, phentermine, orlistat).

Reduction of digoxin dose should be considered because sotagliflozin acts as a weak P-glycoprotein inhibitor and increases systemic exposure to digoxin.

Patients taking sotagliflozin with concomitant digoxin should have digoxin concentrations monitored and doses reduced as needed. In addition, other P-gp substrates may be affected and the labels of P-gp substrate drugs should be consulted with regards to monitoring and dose adjustments.

Other medications which are unlikely to interfere with the pharmacokinetic (PK) or pharmacodynamics (PD) of the IMP or confound interpretation of the study endpoints are allowed as needed following discussion between the Investigator and the Sponsor/CRO. However, doses of chronically administered medicines should be kept fixed during the trial if at all possible.

The dose of all antihypertensive agents should be kept constant during the 12 weeks following randomization and no antihypertensive agents should be added or withdrawn for the 12 weeks following randomization unless it is considered necessary for safety reasons.

2.1.3 Efficacy endpoints

All efficacy measurements collected during the study will be considered for the analyses, including those obtained after IMP discontinuation, or introduction of rescue therapy (see [Section 2.5.4](#)).

HbA1c, FPG, eGFR, Cystatin C, UGE, UACR, UGCR, Fructosamine, and NT-proBNP are measured/calculated in a central laboratory (see study flowchart in Appendix E). FPG, Cystatin C, Fructosamine, NT-proBNP are measured in the fasting state. Body weight, SBP and DBP (see [Section 2.1.4.5](#)) are measured at on-site visits by the Investigator. Patients requiring rescue

are identified as those with the reason for treatment ticked “rescue therapy” in e-CRF “Medication” page.

Efficacy variables will be summarized in both standard international units and conventional units when applicable.

2.1.3.1 Primary efficacy endpoints

Change from Baseline to Week 26 in HbA1c (%) comparing sotagliflozin 400 mg versus placebo in overall population, and in CKD Stages 3A and 3B patients sequentially, then comparing sotagliflozin 200 mg versus placebo in overall population, and in CKD Stages 3A and 3B patients sequentially.

2.1.3.2 Secondary efficacy endpoints

To compare sotagliflozin 400 mg and 200 mg versus placebo, respectively, in terms of:

- Change from Baseline in FPG at Week 26.
- Change from Baseline in body weight at Week 26.
- Change from Baseline in SBP at Week 12 for patients with Baseline SBP \geq 130 mmHg.
- Change from Baseline in SBP at Week 12 for all patients.
- Percentage change in UACR from Baseline to Week 26 for patients with UACR $>$ 30 mg/g at Baseline.
- Proportion of patients with HbA1c $<$ 6.5%, $<$ 7.0% at Week 26.

2.1.3.3 Other efficacy endpoints

To compare sotagliflozin 400 mg and 200 mg, respectively, versus placebo in terms of:

- Change from Baseline in SBP at Weeks 26 and 52 for patients with Baseline SBP \geq 130 mmHg.
- Change from Baseline in SBP at Weeks 26 and 52 for all patients.
- Change from Baseline in HbA1c at Week 52.
- Change from Baseline in FPG at Week 52.
- Change from Baseline in body weight at Week 52.
- Change from Baseline in eGFR.
- Proportion of patients requiring rescue for hyperglycemia during 26-week double-blind Treatment Period.
- Change from Baseline in:
 - Cystatin C,
 - UGE,

- UGCR,
- Fructosamine,
- NT-proBNP.
- Proportion of patients with progression to end-stage renal disease (ESRD) (dialysis or transplant) at Week 4 or any time later during the trial.
- Proportion of patients with >50% decline in eGFR from Baseline to Week 26 and Week 52.
- Proportion of patients with progression from normal to microalbuminuria or from microalbuminuria to macroalbuminuria from Baseline at Week 26 and Week 52.
- Proportion of patients with improvement from microalbuminuria to normal or from macroalbuminuria to microalbuminuria from Baseline at Week 26 and Week 52.
- Change from Baseline in SBP at Week 12 for patients with Baseline SBP <130 mmHg.
- Change from Baseline in DBP at Week 12 for all patients and the subset of patients with Baseline DBP \geq 80 mmHg.

2.1.4 Safety endpoints

The safety analysis will be based on the reported adverse events, hypoglycemia, acute renal failure, and other safety information, such as clinical laboratory data, vital signs, electrocardiogram (ECG), bone mineral density (BMD) results, physical examination, and marker of intestinal transit and absorption, markers of bone and calcium metabolism, etc.

Observation period

The observation period will be divided into 4 epochs:

- The **screening** epoch is defined as the time from the signed informed consent date up to the first administration of the double-blind IMP.
- The **treatment** epoch is defined as the time from the first administration of the double-blind IMP to the last administration of the double-blind IMP. This epoch includes the 26-week double-blind core treatment period and the 26-week double-blind extension treatment period. The 26-week core treatment period is the time from the first administration of double-blind IMP to the last administration of double-blind IMP on or before Visit 9/Week 26 (or Day 182 if Visit 9/Week 26 date is missing).
- The **residual treatment** epoch is defined as the time from the last administration of the double-blind IMP up to 10 days (1 day for hypoglycemia) after the last administration of the double-blind IMP.

The treatment-emergent adverse event (TEAE) period will include both **treatment** and **residual treatment** epochs (See TEAE period for the 26-week core treatment period in [Section 2.5.4](#)).

- The **posttreatment** epoch is defined as the period of time starting the day after the end of the treatment-emergent adverse event period up to the last protocol-planned visit or the

resolution/stabilization of all serious adverse events (SAE), adverse events of special interest (AESI) and events of special interest (EOSI), whichever is later.

The on-study observation period is defined as the time from start of double-blind treatment until the end of the study (defined as the last scheduled visit for those who completed the study and the date collected on e-CRF page “Completion of End of Study/Follow-up” for those who did not complete the study).

The post-study observation period is defined as the time from the day after the end of the study until the resolution/stabilization of all SAE, AESI and EOSI if applicable.

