	
when reaching the target number as planned.
 
Following randomization, patients will have a 26-week double-blind Treatment Period, followed by a 26-week double-blind Extension Period, and a 4-week post-treatment Follow-up Visit to collect safety and some efficacy information.
 
Patients will be monitored throughout the double-blind Treatment Period and Extension Period for signs of deterioration in renal function (eg, decrease in eGFR) as well as all other routine clinical and laboratory findings. If at any visit after Randomization up to Week 8 there is a rise in creatinine level (ie, >50% increase from Baseline level, where Baseline level is defined as the mean of creatinine values obtained at Screening and Randomization) or if at any visit after Week 8 there is a rise of >50% above the mean of creatinine values from the previous 2 visits, the Investigator should ensure that no reasonable explanation exists for creatinine increase and in particular the following causes:
 

• Medications that increase creatinine

• Decrease in cardiac output

• Obstructive uropathy

• Urinary tract infection

• Volume depletion.

 
If addressing these causes does not reduce the creatinine level below the above stated threshold, the investigational medicinal product (IMP) will be stopped for 2 weeks. If at creatinine recheck the patient has returned to the below threshold, then IMP will be restarted at a reduced dose (ie, dose reduced via interactive response technology to 200 mg for those randomized to 400 mg, maintained to 200 mg for those randomized to 200 mg, and to placebo for those randomized to placebo). If the creatinine does not return to below the threshold, the IMP will be permanently discontinued but the patient will be asked to continue attending all study visits.
 
The HbA1c and FPG results will be masked to study sites and patients after randomization and until study end. To prevent partial unblinding, UGE and UGCR results will also be masked to study sites and patients. Additionally, urinalysis by dipstick will not include the measurement of urine glucose.
 
Quantitative urine glucose, albumin, calcium, phosphorus, magnesium, and creatinine will be measured separately at all on-site visits by the central laboratory.
 
Early termination
 
If a patient discontinues treatment with IMP early during the Treatment Period, the patient will have a Premature End of Treatment (EOT) visit and a Follow-up Visit 4 weeks after the last dose of IMP. In addition, every effort will be made to have all patients return to the site at the time corresponding to their scheduled visits, particularly the Week 26 and Week 52 visits.
 
If a patient does not agree to site visits, he/she will be contacted by telephone to enquire about their safety information, particularly at the time of the initially scheduled end of study.

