#### 8.1.1 Dose reduction

The dose maintenance will be handled according to the renal function assessed by the creatinine measurement throughout the study. If at any visit after Randomization there is a rise in creatinine level (see details in Section 10.6.2), the Investigator should ensure that no reasonable explanation exists for creatinine increase. Sites will be notified by central laboratory alert if a patient has a >50% increase from Baseline level or >50% above the mean of creatinine values from the last

2 visits, where Baseline level is defined as the mean of creatinine values obtained at Screening and Randomization. The IMP should be stopped for 2 weeks. If at creatinine recheck the patient has returned to the below threshold then IMP will be restarted at a reduced dose (ie, dose reduced via IRT to 200 mg for patients randomized to 400 mg, maintained to 200 mg for patients randomized to 200 mg, and to placebo for patients randomized to placebo). Since IMP received is blinded, patients must return to the site and IRT will be contacted for this IMP re-initiation. Dose reduction can only be obtained at on-site visit by IRT. If the creatinine does not return to below the threshold, the IMP will be permanently discontinued but the patient will be asked to continue attending all study visits.

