### **Observation period of safety endpoints**

The observation period of safety data will be divided into 3 segments:

- The pre-Treatment Period is defined as the time between the date of the informed consent and the first dose of double-blind IMP
- The on-Treatment Period (TEAE period) is defined as the time from the first dose of double-blind IMP up to 10 days (1 day for hypoglycemia) after the last dose of double-blind IMP, regardless of the introduction of rescue therapy. The 10-day interval is chosen based on the half-life of the IMP (approximately 5 times the half-life of sotagliflozin) in patients with moderate renal dysfunction
- The post-Treatment Period is defined as the time starting 11 days after the last dose of double-blind IMP (after the on-Treatment Period).

The Baseline value for safety endpoints in the safety population is the last available value (or the average of all values for creatinine or eGFR) prior to the first administration of the double-blind IMP.

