#### **10.3.1 Temporary treatment discontinuation with investigational medicinal product**

Temporary treatment discontinuation may be considered by the Investigator because of suspected AEs.

Lower extremity complications (such as skin ulcers, infection, osteomyelitis, and gangrene) requiring treatment should lead to temporary discontinuation of IMP.

If at any visit after Randomization up to Week 8 there is a rise in creatinine level (ie, >50% increase from Baseline level, where Baseline level is defined as the mean of creatinine values obtained at Screening and Randomization) or if at any visit after Week 8 there is a rise of >50% above the mean of creatinine values from last 2 visits, the Investigator should ensure that no reasonable explanation exists for creatinine increase.

The IMP should be stopped for 2 weeks.

Reinitiating of treatment with the IMP will be done under close and appropriate clinical/and or laboratory monitoring once the Investigator has considered according to his/her best medical judgment in the occurrence of the concerned event was unlikely to be related to the IMP and if that the selection criteria for the study are still met (refer to [Section 7.1](#) and [Section 7.2](#)).

If at creatinine recheck the patient has returned to the below threshold then IMP will be restarted at a reduced dose (ie, dose reduced via IRT to 200 mg for those randomized to 400 mg; maintained at 200 mg for those randomized to 200 mg). Since the IMP received is blinded, patients must return to the site and IRT will be contacted for IMP re-initiation.

It is in the interest of the patient to monitor their blood glucose during the temporary discontinuation period, therefore regular determination of SMBG is to be performed and documented (see [Section 9.2.1.8](#)).

For all temporary treatment discontinuations, duration should be recorded by the Investigator in the appropriate pages of the e-CRF when considered as confirmed.

Temporary treatment discontinuation decided by the Investigator corresponds to more than 1 dose not administered to the patient.

Use of any other anti-hyperglycemic medication during the time of temporary treatment discontinuation (ie, insulin during a hospitalization) is to be recorded as concomitant medication with the name and dose recorded in the e-CRF.

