#### **10.3.3 List of criteria for permanent treatment discontinuation**

Patients may withdraw from treatment with the IMP if they decide to do so, at any time and irrespective of the reason, or this may be the Investigator's decision. Patients should discuss stopping study medication with the site before doing so in order that questions can be addressed, glycemic therapy adjusted, and a follow-up assessment arranged. All efforts should be made to document the reasons for treatment discontinuation; this reason should be documented in the e-CRF.

The following reasons can lead to permanent discontinuation:

- At the patient's own request (ie, withdrawal of consent for treatment).
- If, in the Investigator's opinion, continuation with the administration of the study treatment would be detrimental to the patient's well-being.
- Intercurrent condition that requires permanent discontinuation of the study treatment as long as the abnormality persists and if the casual relationship of the concerned event and the IMP is possible (according to the Investigator's best medical judgment).
- Deterioration of renal function (defined as increase in serum creatinine > 50% from Baseline) that is not recovered after a temporary IMP discontinuation for 2 weeks.
- Patient requires renal replacement therapy (transplant or dialysis).
- Pregnancy (in female patients).
- Specific request of the Sponsor.

Any abnormal laboratory value will be rechecked immediately to confirm the result before a decision is made to permanent discontinue IMP for the concerned patient.

For patients who prematurely discontinue the IMP, the assessments planned at EOT visit ([Section 10.1.3.2](#)) will be performed at the Premature EOT Visit scheduled preferably prior to treatment discontinuation or as soon as possible after the time of discontinuation (at the latest at the next scheduled on-site visit). In the case of premature IMP discontinuation, no sample for measuring plasma concentration should be taken at the Premature EOT Visit, or at any subsequent

visit. The reason(s) for IMP discontinuation will be clearly specified. This Premature EOT assessment may occur at a regularly scheduled or at an unscheduled visit.

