2.4.5.4 Analyses of laboratory variables

Laboratory parameters will be grouped and summarized by biological function as described in [Section 2.1.4.4](#).

The summary statistics (including number, mean, median, Q1, Q3, standard deviation, minimum and maximum) of all laboratory variables (central laboratory values, changes from baseline, and/or percent change from baseline [eg, lipid parameters, albumin, total protein, hemoglobin, hematocrit]) will be calculated for each applicable visit or study assessment (screening, baseline, post-baseline time point, last on-treatment value) by treatment group. Graphical presentations may be used to examine trends over time using mean (\pm SE) and/or mean change from baseline (\pm SE) at scheduled visits (eg, creatinine, eGFR).

The incidence of PCSAs (list provided in Appendix A) at any time during the treatment-emergent adverse event period will be summarized by biological function and treatment group whatever the baseline level and/or according to the following baseline status categories:

- Normal/missing.
- Abnormal according to PCSA criterion or criteria.

For creatinine, $\geq 50\%$ change from baseline will be provided in addition to the PCSA criteria defined, ie, $\geq 150 \mu\text{mol/L}$ (Adults), $\geq 30\%$ change from baseline, $\geq 50\%$ change from baseline, and $\geq 100\%$ change from baseline will be presented. For eGFR, $\geq 50\%$ decrease from baseline will be provided in addition to the PCSA criteria defined, ie, < 15 (end stage renal disease), $\geq 15 - < 30$ (severe decrease in GFR), $\geq 30 - < 60$ (moderate decrease in GFR), $\geq 60 - < 90$ (mild decrease in GFR), and $\geq 50\%$ decrease from baseline will be presented. For parameters for which no PCSA criteria are defined, similar table(s) using the normal range will be provided.

All measurements collected during the TEAE period, including values from unscheduled visits, will be considered for the PCSA summaries. The summary tables will include patients in the safety population that have at least 1 assessment performed during the TEAE period. When a PCSA definition involves a change from baseline value, patients must also have a baseline value to be included in the summaries, and when required by the definition of the abnormality, patients must also have available laboratory normal ranges.

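### The recheck that ends a creatinine pause counts as on-treatment if IMP is restarted and post-treatment if it is not, so the on-treatment renal abnormality tables can undercount the severest rows (minor)

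*SAP*

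**What the plan says.** **The pause.** Once the creatinine rule is met, Protocol 10.3.1 states: "The IMP should be stopped for 2 weeks". The Clinical Trial Summary gives the same length ("the investigational medicinal product (IMP) will be stopped for 2 weeks").

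**The decision after the pause.** If creatinine has recovered, the Clinical Trial Summary says: "If at creatinine recheck the patient has returned to the below threshold, then IMP will be restarted at a reduced dose". If it has not, Protocol 8.1.1 says: "If the creatinine does not return to below the threshold, the IMP will be permanently discontinued". Protocol 10.3.3 describes the second case as deterioration "that is not recovered after a temporary IMP discontinuation for 2 weeks", which puts the deciding recheck after the pause. No exact recheck day is fixed. Protocol 10.3.1 also makes restart depend on the investigator judging the event unlikely to be IMP-related and on the selection criteria still being met.

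**The window.** SAP 2.1.4 runs the treatment epoch from first to last dose, without removing interruptions, and adds a residual epoch "up to 10 days (1 day for hypoglycemia) after the last administration of the double-blind IMP". Protocol 9.2 agrees: "The post-Treatment Period is defined as the time starting 11 days after the last dose of double-blind IMP".

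**The tables.** SAP 2.4.5.4 states: "All measurements collected during the TEAE period, including values from unscheduled visits, will be considered for the PCSA summaries". The creatinine rows are at least 150 µmol/L and rises of at least 30%, 50% and 100% from baseline. The eGFR rows are the absolute bands plus a fall of at least 50%. Neither document has a rule that places the post-pause recheck in the on-treatment period.

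**The concern.** The same protocol-mandated measurement is put in different analysis periods according to what follows it, and what follows depends mainly on its own result. A recheck below threshold that leads to restart stays on-treatment. A recheck still above threshold becomes post-treatment. SAP 2.4.5.4 intends unscheduled values to count toward the PCSA tables, so the exclusion looks like an unforeseen effect of two clocks, 14 days and 10 days, that were set independently.

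At stake is the count of patients in the severest creatinine and eGFR rows, in a trial whose population has moderate renal impairment. A renal adverse event that first starts or worsens after Day 10 in a non-restarted patient likewise leaves the treatment-emergent tables, including the acute renal failure summary in SAP 2.4.5.2.

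**Working it through.** The plan states no figure for this point, so there is none to reproduce. The check is day arithmetic plus the SAP's own eGFR formula.

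**Step 1: dates.** Take the last dose before the pause as Day 0.

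| | IMP restarted | IMP not restarted |
|---|---|---|
| Last dose | after the recheck | Day 0 |
| Treatment-emergent period ends | 10 days after that later dose | Day 10 |
| Post-treatment period starts | correspondingly later | Day 11 |
| Recheck (2 weeks = Day 14 or later) | on-treatment | post-treatment, at least 14 − 10 = 4 days outside |

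Only a recheck by Day 10 would stay on-treatment in a non-restarted patient, and that would be before the 2-week pause had run.

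**Step 2: can the trigger value alone fill the severe rows?** In SAP 2.5.1, eGFR is proportional to creatinine raised to the power −1.154. The age, sex and race terms cancel within a patient over a short interval, so eGFR ratio = (creatinine ratio)^−1.154.

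- At the trigger, 1.5-fold: 1.5^−1.154 = 0.626, a 37% fall.
- At 1.8-fold: 0.507, a 49% fall.
- At 2.0-fold: 0.449, a 55% fall.
- Creatinine ratio needed for a 50% eGFR fall: 2^(1/1.154) = 1.82.
- Creatinine ratio needed for the 100% row: 2.0.
- Band below 15: 15 / 0.626 gives 23.9, so a value exactly at the trigger reaches this band only from a baseline eGFR under about 24. Entry requires at least 30.

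A patient can therefore trigger the pause without reaching the 100% creatinine row, the 50% eGFR row or the lowest eGFR band. As an illustration, suppose creatinine is 1.8-fold at the trigger and 2.0-fold at the recheck. On-treatment, the patient counts in the 30% and 50% creatinine rows. The 100% creatinine row and the 50% eGFR row are reached only at the recheck and are not counted.

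These ratios are to baseline. Up to Week 8 the trigger is also defined against baseline. After Week 8 it is defined against the mean of the previous two visits, so the ratio to baseline at the trigger can be lower or higher than 1.5.

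**Step 3: direction.** The PCSA tables count a patient with at least one qualifying value. Adding an excluded recheck can put a patient into a row but cannot remove one. The effect is therefore an undercount or nothing.

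**Step 4: other laboratory tables.** Under SAP 2.5.4 and 2.5.5, unscheduled values enter by-visit summaries only when they fall on a scheduled date or replace a missing scheduled value. Among the treatment visits, only Weeks 2 and 4 are two weeks apart. Most rechecks stay out of the by-visit tables whether or not IMP is restarted.

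**The case against.** The case for leaving the plan alone is substantial.

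- **The window is deliberate.** Protocol 9.2 sets 10 days at about five half-lives, which implies a half-life of about 2 days. A Day 14 recheck is off-drug. This stands, and it is a reason not to move the window.
- **The trigger is normally counted.** It precedes the last dose. Up to Week 8 it is more than 50% above baseline, so it fills the 30% and 50% creatinine rows. This stands for the lower rows. After Week 8 it is not guaranteed.
- **Other analyses cover part of the gap.** SAP 2.1.3 keeps efficacy values after discontinuation. SAP 2.4.4.3 tabulates eGFR decline above 50% at each scheduled visit and plots time to first occurrence to end of study, with censoring at end of study in Table 5. This covers lasting falls. SAP 2.5.4 gives scheduled values precedence, so a transient peak at an unscheduled recheck could still be missed, and the creatinine categories have no on-study counterpart.
- **The data remain visible.** Patients with any PCSA are listed with their full profile, dose interruptions for creatinine are counted by arm, and post-treatment adverse events are tabulated separately. This stands, but a listing or a separate period is not an arm-level count.

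A reader might infer that the laboratory picture is tilted toward reversible rises. The documents do not support that. The PCSA tables record any occurrence and do not show reversibility, and a favourable recheck cannot take a patient out. The last on-treatment value does not conceal the rise either: under SAP 2.4.5 it is the value at, or closest before, the last dose, which for a non-restarted patient is typically the trigger value.

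**Conclusion.** The gap is real and minor. The recheck's period is set by whether IMP is restarted, which depends mainly but not only on creatinine recovery: a patient who recovers but is not restarted under Protocol 10.3.1 also has a post-treatment recheck.

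Two consequences follow. A non-restarted patient who first reaches a higher PCSA category at the recheck is missing from that row. A renal adverse event that first starts or worsens after Day 10 is missing from the treatment-emergent tables. Both act in one direction. By-visit tables are little affected.

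It is tempting to attach a number of lost patients per arm. Neither document gives a trigger rate, a non-recovery rate or the share who first cross a category at the recheck, so no count is supported. A count of rechecks outside the window would in any case exceed the number of patients missing from a row. The conclusion rests on the plain reading that the recheck comes after the 2-week pause, on Day 14 or later.

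**What to change.** In SAP 2.4.5.4, add a table by arm over the on-study observation period already defined in SAP 2.1.4, placed beside the treatment-emergent one. It should show the creatinine categories (at least 150 µmol/L; rises of at least 30%, 50% and 100% from baseline) and the eGFR categories, including a fall of at least 50%. State that unscheduled values and rechecks after an interruption are included. In the PCSA listing, flag rechecks that follow a creatinine interruption.

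Leave the 10-day window unchanged. Extending it only for patients who are not restarted would still depend on outcome and would reclassify all their adverse events in the added days. The on-study table applies the same rule to every patient. SAP 2.4.5.2 already counts amputations on this kind of basis, regardless of on- or post-treatment timing.

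The cost is one repeated descriptive table and a listing flag. The downside is that the new table includes some off-drug values and should be labelled accordingly. The pause, restart and discontinuation rules are not touched.
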